5.15. Data analysis

5.15.1. Key questions for TRACK-HD across assessment domains

1. A key question for Track-HD was "What individual or composite measure within each assessment domain shows the greatest change (largest effect sizes) over a one year time period?" Based on previous results from TRACK-HD, it is now possible to recommend a range of objective, quantifiable outcome measures for clinical trials in early stage HD participants over a realistic timeframe and with practical sample sizes (Tabrizi et al. 2011, Tabrizi et al under review Lancet Neurology). However, this question remains for potential disease modifying treatments in premanifest HD.

- 2. For those measures with the largest longitudinal effect sizes, what sample sizes are needed over what intervals to detect disease modifying effects?
- 3. How do domain specific effect sizes per interval compare and how might data be combined across domains to reduce redundancy, enhance the variance for which we can account, and ultimately increase efficiency of clinical trials?

Analytical comments:

- a) Within the bounds set by recruitment guidelines, participants in Track-HD are at arbitrary points in the HD development trajectory. Therefore, the annual slope estimated by ongoing modelling longitudinal change provides an estimate, statistical significance, and implicit power information regarding rates of one year change. However, it must be recognized that repeated measurement effects such as learning effects may have an impact on some of the measurements. This is known to be an issue for many cognitive measures. (See 5.15.7 below.) Therefore, we will also conduct secondary analyses looking specifically at observed effects over only the first year of any new assessment in order to test the consistency of inference from future observations. Longitudinal analysis will proceed along guidelines outlined in 5.14Error! Reference source not found. even in this case, with the results obviously directly applicable to the one-year hypothesis.
- b) The general strategy outlined in 5.14 will provide estimates and standard errors of longitudinal change, variance, and within-participant covariance for each outcome. These will be readily combinable with hypothesized treatment effects to estimate sample size/durations, with confidence intervals, for future clinical trials. The approach is the same that [name] used (section 5.16.2) to advise on sample size for Track-HD.
- c) The relevant effect sizes for outcome comparisons are defined by change per unit of time divided by the mean within-participant residual standard deviations. This information is a product of the general analytic approach described above. The combination of longitudinal outcomes is subject to strong caveats discussed above in 5.14. Bearing these limitations in mind, we will attempt to maximize longitudinal variance explained via principal component analysis of the set of standardized change scores, adjusted for background covariates, and via canonical correlation analysis of these change scores and separate, well-validated prognostic variables (at a minimum, with CAG-age estimated probability of onset).

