5.5.7.2. Information on specific instruments

Symbol Digit Modalities Test (SDMT; Total Time Required: 3 minutes)

This is a test of visuomotor integration, involving visual scanning, tracking, and motor speed. The examinee is given 90 seconds to match symbols and digits as quickly as possible. The key (specifying which number corresponds to each symbol) is located at the top of the page (Smith, 1991).

Likely main variable for analysis: Total number of correct responses.

Rationale and strength of evidence for the selection of SDMT

HD Toolkit meta-analysis suggests that SDMT performance declines longitudinally in both Premanifest HD Near Onset and Early HD (Figure 4). In Premanifest HD, SDMT also provides unique ability to predict probability of onset within 5 years ([name] et al., 2004) beyond that of the other tasks in the proposed core cognitive battery. In TRACK-HD, the SDMT has showed differences in rates of change at both 12, 24 and 36 months in early HD, and also had one of the largest effect sizes in premanifest HD of 0.20 (95% CI: -0.03 to 0.43) over 12 months and 0.14 (95% CI: -0.11 to 0.38) over 24 months, although these were not significant.

Stroop Word Test (Total time required: 2 minutes)

The Stroop Test has three conditions that require visual scanning, cognitive control and processing speed. Because the Word Reading condition (the first condition normally presented) is the most sensitive in premanifest HD, it is the only Stroop condition that will be used in the Track Cognitive battery. Participants are given a card on which the names of colors are printed in black ink and must read as many words as they are able in 45 seconds.

Likely main variable for analysis: Number of words read correctly in 45 seconds

Rationale and Strength of Evidence

HD Toolkit meta-analysis suggests that performance on the Stroop Word Test deteriorates longitudinally in both premanifest (Predict-HD) and Early HD (Figure 4). Longitudinal studies are supported by a consistent pattern of results in cross-sectional studies of premanifest and early HD and sizeable correlations in premanifest HD with time to onset (ES=0.54, p<.001) and neuropathology/striatal volume (ES=0.35, p<.001); and in early HD with striatal volume (ES=-0.35, p<.001). Furthermore, in premanifest HD, Stroop Word provides unique ability to predict UHDRS motor score beyond that of the other tasks in the proposed core cognitive battery.

Self-Paced Tapping (Total time required: 4 minutes)

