In TRACK-HD, circle tracing detected differences in rates of change at both 12 and 24 months in early HD, and, together with SDMT, had one of the largest effect sizes in premanifest HD of 0.23 (95% CI: -0.03 to 0.51) over 12 months and 0.19 (95% CI: -0.10 to 0.48) over 24 months, although these were not significant. The test has therefore been recalibrated with the aim of increasing sensitivity in the premanifest population.

Analysis of current longitudinal data for the Circle Tracing task shows that the indirect condition is showing evidence of plateauing in longitudinal performance for controls and convergence of the premanifest HD groups at visit 5, and accordingly, it has small effect sizes. The Circle Tracing task will therefore be discontinued at V7 in order to interrogate the data.

Circle Tracing with Counting Backwards (Total time required: 4 minutes)

This condition is added to the existing circle tracing task in which participants perform the circle tracing task while at the same time counting backwards condition (e.g. counting from 100 backwards by 3s). The participant traces a 90mm diameter circle on a horizontal computer tablet while trying to remain within a 5 mm error margin that is indicated by a white annulus on a grey background. The participant attempts the task while indirectly viewing stylus movement on a separate, vertical computer screen with hand and stylus movement occluded from view (3 trials, 45 seconds each). The counting backwards component of this task requires participants to count aloud backwards by some number while performing the Circle Tracing task. Prior to combining circle tracing and counting backwards, participants will practice counting backwards alone.

Data generated for this task: Speed and errors (e.g. number of deviations per rotation)

Visual Array Comparison Task (Total time required: 8 minutes)

This task assesses the ability to sustain object and location representations without the aid of rehearsal and chunking strategies, leaving a purer measure of attentional capacities. This task is thought to be sensitive to a critical bottleneck for executing perceptual and cognitive functions that occurs when it is necessary to extract and retain items in visual short-term memory (on average about 4 items).

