particular, the inferior and superior parietal lobes in healthy controls (Alivisatos & Petrides, 1997; Farah & Hammond, 1988; Harris, et al., 2000; Ng, et al., 2000; Zacks, 2008).

Very little is known about mental rotation abilities in participants presymptomatic for HD. One small cross sectional study using a mental rotation task with the Shepard and Metzler cube stimuli showed a respectable effect size in a small sample of PreHD near-to-onset participants (ES = -0.68; nHD = 11, ncontrol = 31) (Robins Wahlin, Lundin, & Dear, 2007). This task was introduced at Year 3 of TRACK-HD and cross-sectional data showed impaired accuracy in both early stage and premanifest participants.

Figure 3 A normal and mirror stimulus from the Mental Rotation 3D task

Cancellation Test (Total time required: 6 minutes)

This task measures selective attention. Across several trials (typically 3 90-sec trials), participants must locate particular stimuli or combinations of stimuli (for example small squares with a small line on a given side, or pictures of fruits) randomly distributed among distractors (squares with a line on another side, pictures of other fruits or other similar looking objects) on a tablet computer.

Data generated for this task: speed, correct identifications and errors

When comparing effect sizes using the available cross-sectional data, the digit condition was found to have larger effect sizes compared to the figure condition, and when comparing significant group differences from p-values, the digit condition showed more significant group differences than the figure condition. It has therefore been decided that the figure condition of the Cancellation task will be removed from the V7 cognitive battery, leaving only the digit condition,

Virtual Maze task (Total time required 20 mins)

This task measures spatial navigation using a virtual environment presented on a computer screen. Participants are required to navigate through the virtual environment in the shortest possible time to a particular target, from differing locations and through varied environments.

Data generated for this task: number of trials completed, choice accuracy, error rate, latency.

Rationale and strength of evidence

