5.15.5. Biomarkers in plasma data analysis

Proteomic, neuroinflammatory, transcriptomic, and metabolic markers identified from our current ongoing biomarker research initiatives will be further validated using the Track-HD plasma and RNA samples. Specific *a priori* candidates will be analyzed using the general longitudinal approach described in 5.14. Any additional screening for new candidate markers will be subject to multiple comparison corrections (e.g. false discovery rate) in assessing the probable statistical and scientific significance of the results. Changes in each of the laboratory biomarkers identified will be correlated with the clinical and imaging phenotypic data using multivariate assessments.

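### Future-trial sample sizes for the measures ranked highest on observed effect size come from the same data with ordinary confidence intervals, so the top estimates are biased upward and the trials sized on them too small

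*Protocol*

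**What the plan says.** Protocol section 5.15.1 opens with the question "What individual or composite measure within each assessment domain shows the greatest change (largest effect sizes) over a one year time period". It regards this as settled for early-stage disease but adds: "However, this question remains for potential disease modifying treatments in premanifest HD". The second key question carries the leaders forward to trial design: "For those measures with the largest longitudinal effect sizes, what sample sizes are needed over what intervals to detect disease modifying effects".

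Analytical comment (b) in the same section gives the method. The longitudinal models yield estimates, standard errors, variances and covariances for each outcome, and: "These will be readily combinable with hypothesized treatment effects to estimate sample size/durations, with confidence intervals, for future clinical trials". Comment (c) defines the effect size as change per unit of time over the mean within-participant residual standard deviation.

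The section describes no step that separates the data used to rank from the data used to estimate, and no adjustment of the estimate or interval for having been ranked first. Other parts of the plan bear on the point:

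- Comment (a) says each slope comes with its statistical significance, and adds a first-year analysis of new assessments because of learning effects.
- Section 5.14.1 says differences from controls must be notable for a marker to be a candidate surrogate. It gives no number.
- Section 5.14.2 undertakes to keep a priori and post hoc hypotheses apart.

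**The concern.** Each observed effect size is a true value plus sampling error. Taking the largest of several favours the measure whose error happened to be positive, so its expected value exceeds the true effect of the measure chosen. An interval built as if that measure had been named in advance is centred too high.

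The required sample size varies with one over the squared effect size, so a modest excess in the effect becomes a large shortfall in the trial. Sizing future premanifest trials is one of the study's stated purposes. A later sponsor who takes the figure at face value would run an underpowered trial, and a real treatment effect could be missed. The bias is worst when many measures have similar, small true effects. That situation is plausible in premanifest disease, where section 5.16 reports few convincing longitudinal differences from controls up to visit 4.

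**Working it through.** The protocol attaches no figure to the selection step, so its size has to be illustrated.

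**Inputs from the protocol**

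- Section 5.5.7.2, SDMT: "also had one of the largest effect sizes in premanifest HD of 0.20 (95% CI: -0.03 to 0.43) over 12 months". The interval is centred on its estimate: (−0.03 + 0.43)/2 = 0.20. SE = (0.43 + 0.03)/3.92 = 0.117.
- Section 5.5.7.2, Circle Tracing: "had one of the largest effect sizes in premanifest HD of 0.23 (95% CI: -0.03 to 0.51) over 12 months". SE = (0.51 + 0.03)/3.92 = 0.138. The smaller SDMT value is used below because it gives less bias.
- Section 5.16: effects detectable at visit 6 are 58% to 80% of those detectable at 36 months. Multiplying the 12-month SE by 0.58 and 0.80 is an assumed allowance for longer follow-up.

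**Assumptions:** 10 measures in a domain, equal pairwise correlation of 0.3 (or 0.6), the same true effect in all, normal estimates.

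**Step 1: expected winner.** The mean maximum of 10 independent standard normals is 1.539. With equal correlation ρ it becomes 1.539 × √(1 − ρ):

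- ρ = 0.3: 1.539 × 0.837 = 1.29
- ρ = 0.6: 1.539 × 0.632 = 0.97

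Simulation agrees (1.289 and 0.972). The expected winner is the true effect plus this number times the SE. For a true 0.20, ρ = 0.3 and SE 0.117: 0.20 + 1.29 × 0.117 = 0.35.

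**Step 2: shortfall in trial size.** Shortfall = (expected winner / true effect)². This holds whatever treatment effect is hypothesised, provided it is the same fraction of the natural change in both calculations.

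| True effect | ρ | SE 0.117 | SE × 0.80 | SE × 0.58 |
|---|---|---|---|---|
| 0.20 | 0.3 | 0.351; 3.1× | 0.321; 2.6× | 0.288; 2.1× |
| 0.20 | 0.6 | 0.314; 2.5× | 0.291; 2.1× | 0.266; 1.8× |
| 0.10 | 0.3 | 0.251; 6.3× | 0.221; 4.9× | 0.188; 3.5× |
| 0.10 | 0.6 | 0.214; 4.6× | 0.191; 3.7× | 0.166; 2.8× |

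Each cell gives the expected winner, then the factor by which the trial is too small.

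**Step 3: power lost.** A trial planned for 80% power at two-sided 0.05 has a standardised signal of 1.96 + 0.84 = 2.80. If the winner is 0.351 and the truth 0.20, the real signal is 2.80 × 0.20/0.351 = 1.60, and power is Φ(1.60 − 1.96) = 36%. With the SE scaled by 0.80 and 0.58, power is 41% and 49%.

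**Step 4: what the ordinary interval does.** A 95% interval's lower limit should lie below the truth in 97.5% of studies. For the best of 10 equal measures it does so in 78% (ρ = 0; exactly 0.975¹⁰ = 0.776), 82% (ρ = 0.3) or 87% (ρ = 0.6). A sample size with an ordinary interval is therefore optimistic at both its centre and its edge.

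**The case against.** The best defence is that section 5.15.1 poses research questions and is not a decision rule. The overall key question (sections 4.13 and 5.3) concerns a combination of measures. Comment (b) gives estimates for each outcome, and section 5.15.9 sizes trials on every imaging measure, so sizing is not confined to winners. A separate analysis plan could add thresholds. All of this is fair, and the lack of a stated threshold is not the finding. The point is narrower: where measures are singled out by rank, the method described yields estimates and intervals that ignore the ranking.

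The illustration also assumes equal true effects, the case in which selection bias is greatest. A measure that truly stands clear of the rest would show much less bias. That limits the size but leaves the direction unchanged.

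A reader might infer four stronger things that the documents do not support:

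- **That the plan is bound to promote a useless measure because some measure always ranks first.** Any list has a maximum. Slopes come with significance, sample sizes with intervals, and differences must be notable. The protocol's own record is sober: sections 5.5.7.2, 5.2 and 5.16 describe the leading premanifest cognitive results as non-significant or unconvincing.
- **That SDMT and Circle Tracing were chance findings because their effects were lower at 24 months than at 12** (0.14 against 0.20, and 0.19 against 0.23). Comment (c) defines effect size per unit of time, so steady decline need not raise it. The scaling of these figures is not stated, and the falls lie well inside the intervals.
- **That the choice between Cancellation conditions is an example** ("when comparing significant group differences from p-values, the digit condition showed more significant group differences than the figure condition"). That comparison is cross-sectional and within one task.
- **That section 5.15.5 already sets a false-discovery rule for the established battery.** It reads "Any additional screening for new candidate markers will be subject to multiple comparison corrections (e.g. false discovery rate" and applies to additional laboratory screening; specific a priori candidates go through the general longitudinal approach. Extending it to whole domains would be a debatable choice.

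**Conclusion.** The concern holds as a bias in estimation. For measures picked by rank, the effect sizes that feed trial planning are too large on average and their ordinary intervals too optimistic. With 10 measures, correlation 0.3 and a shared true effect of 0.20, the trial is about 3 times too small at the 12-month precision, and about 2 to 2.6 times too small with the standard error reduced for longer follow-up. Over the whole table the factor runs from 1.8 to 6.3. These sizes rest on an assumed number of measures, correlation and equality of effects, and on carrying the visit-6 ratio over to a 12-month standard error.

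The first-year analysis, the demand for notable differences and the a priori/post hoc distinction do not correct the bias. The first targets learning effects, the second has no number, and the third does not help when ranking is itself the planned analysis. The documents do not show that the study would recommend a measure with no true change.

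**What to change.** Add to section 5.15.1, or to the analysis plan that implements it:

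1. For any measure chosen by rank, report the effect size, trial sample size and interval after correcting for selection. The general method is to resample participants and repeat the whole ranking step in each bootstrap sample. For continuing measures an alternative is to select on visits 1–4 and estimate on visits 5–7. Many participants contribute to both halves, so the two are not fully independent, and measures introduced at visit 5 or later can use only the bootstrap.
2. Give a bootstrap interval for the rank of each measure, so that near-ties are visible.
3. If the selection-corrected interval of the leading measure includes zero, state that no measure in that domain has been shown to be sensitive.

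The cost is wording and computation, with no new data or visits. Reported effect sizes will be somewhat smaller and the resulting trial sizes larger.

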5.15.2. Secondary questions for TRACK-HD

- 1. What is the earliest point during the premanifest disease process at which longitudinal effect sizes for any measure become sufficient to useful in a clinical trial?
- 2. What are the key demographic and clinical variables that must be taken into account to maximize measure sensitivity, such as age, education level, IQ, sex, etc.?

Analytical comments:

- a) It will be impossible to know the true time from diagnosis for premanifest participants who do not show substantial signs of developing illness during the course of the study. Therefore, estimates of earliest detectable longitudinal changes will rely partly on comparisons to separate, already validated prognostic indicators. For example, we will test relationships between longitudinal change and CAG-age based estimated time until diagnosis and striatal volumes.
- b) As discussed in 5.14, potential demographic and clinical confounders, as identified by the investigators, will be controlled as statistical covariates in the longitudinal and other analytical models.

Revised: 2nd September 2013 73 Version 5.2

